A Randomized Controlled Trial With Retention Testing to Determine the Most Effective Intervention for
Hemorrhage Control Readiness for Laypersons: The PATTs Trial

January 29, 2018

Study Protocol and Statistical Analysis

a. Study design:

- a. Prospective, randomized, multi-arm, open-label trial with follow-up retention testing

b. Location:

- a. Gillette Stadium, Foxborough, Massachusetts, USA.

c. Consent:

- a. Participation in the study was voluntary and oral consent was obtained from all subjects. A fact sheet was provided to all participants.

d. Inclusion/Exclusion criteria:

- a. Adult (18 years and above) volunteers with no prior hemorrhage control training or experience were included in the trial.
- b. Anyone with previous formal hemorrhage control or tourniquet training was excluded from the trial analysis.

e. Randomization:

1. Eligible study subjects were randomized into the following arms using block randomization such that for every four participants, one was randomized to each of the four arms:

- i. **Control arm:** Study subjects in this arm of trial received no intervention (no training or access to point-of-care prompts) to assess baseline competence in hemorrhage control.
- ii. **Experimental arm 1:** Study subjects in this arm were given the American College of Surgeons Bleeding Control Basic (B-Con) in-person training course by qualified instructors. This curriculum was developed by a collaboration between American College of Surgeons and the Hartford Consensus.⁹ The session included a multimedia presentation in a class format that included some background information about extremity hemorrhage and potential benefits of immediate first-response and hemorrhage control, steps to take in a mass casualty scenario and instructional videos on hemorrhage control modalities and their appropriate use. This was followed by hands on training in hemorrhage control, with 1:4, instructor to trainee ratio.

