- iii. **Experimental arm 2:** Study subjects in this arm received a commercially available audio bleeding control kit. The kit included diagram and visual aids to identify the correct severity of injury and determine the appropriate method of bleeding control. The kit also had buttons on it to play stepwise audio instructions on application of compression dressing, hemostatic packing and tourniquet application in two languages (English and Spanish). The audio kits were bought at market price and the name of the manufacturer was not mentioned in the manuscript to avoid conflict of interest.
- iv. **Experimental arm 3:** Study participants in this arm of the trial received bleeding control flashcards that contain diagrams and figures to correctly identify the severity of injury and visual instructions on appropriate application of pressure dressing, hemostatic packing and tourniquet.

f. Sample size calculation:

- a. Sample Size calculation was done using Stata v14.1 with 80% power and an alpha level of 0.05. Trial arm paired-comparisons were taken as independent trials and sample size was calculated for each pair. The largest number was taken as the sample size for each arm. The smallest difference in application rate, and the arm used to determine sample size calculation, was between the control and flashcard arm.
 - i. Control group expected application rate 20% based on prior studies
 - ii. Flashcard Proportion expected application rate 44% based on prior studies
- b. Final sample size is 412 with 103 subjects in each arm. This is before exclusion of individuals with prior hemorrhage control training thus, to account for 20% of individuals to report prior training, over 125 individuals will be recruited to each arm.

g. Pre-study questionnaire:

- a. Study subjects were given a pre-trial questionnaire to gather information regarding age, gender, level of education, any prior first-aid training, and if they reported prior first-aid training, whether it included hemorrhage control training. Those individuals who reported prior hemorrhage control training were then asked an open ended question about what that training consisted of. The questionnaire also included questions to determine participants willingness to assist in an emergency and self-reported comfort level in acting as a first-responder in a mass causality scenario. Answers were presented on a Likert-type scale.

h. Post-trial questionnaire:

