1. After testing of the two point of care prompt arms and the control arm, these individuals then underwent the ACS B-Con training from qualified instructors. This training was 45 to 60 minutes long, consisting of an audio-visual presentation with tourniquet application instructions followed by hand-on training under the supervision of an instructor, the same as the B-Con intervention arm.
2. ***Test for retention:***
 - a. 3-9 months after the trial, we planned to test all study subjects with a simulated mass causality scenario for retention of knowledge and skills. This test will be the same as the initial test for competence at tourniquet placement in the trial and the same evaluation form will be used to evaluate the study subjects.

j. Donation of study material:

- a. At the end of the retention study, the bleeding control boxes will be donated to the stadium, to be co-located with AEDs.

1) ***Statistical analysis:***

- a) The primary outcome in our study was the correct application of tourniquets. The main analyses in the randomized study were the pairwise comparisons of the proportion of correct tourniquet application in each of the three intervention arms to the control arm.
- b) In the initial testing phase, the proportion of participants who correctly applied a tourniquet in the three intervention arms were compared to control using three pairwise two-sided Fisher's Exact Test of the three interventions to control in an intent-to-treat analysis (as randomized).
- c) To analyze retention, we performed two pairwise comparisons: 1) all participants tested at retention versus initial control to identify long-term efficacy (correct tourniquet application) compared to no training; 2) participants tested at retention versus initial testing in B-Con randomized arm to identify if there is a significant skill decay 3-9 month after training. Generalized estimating equations z-tests were used in these pairwise tests to account for the repeated measures on participants who were in both the initial and retention phases.
- d) At retention testing, an a priori planned logistic regression analysis was performed to identify any demographic associations with correct tourniquet application between 3 and 9 months after B-Con training. It also assessed for different effects due to the original (randomized) arm in initial testing in case the combination of randomized arm and then

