B-con training had differential effects on correct tourniquet application (although our a priori hypothesis was that there would be no difference). Age was divided into categorical variables creating three groups using previously defined age breaks: young adult [18-35 years old (yo)], middle aged adult (35-55 yo), and older adult (> 55 yo). This model assessed for an association between days since training to retention testing, allowing for a non-linear effect. We assessed for co-linearity, and interactions between variables [age and education, age and sex, age and prior training, sex and education, sex and prior training] and ran diagnostics on the model fit. We used Hosmer and Lemeshow's goodness-of-fit test to evaluate our model.

- e) The Wilcoxon rank sum test was used to compare time to correct tourniquet application across arms (restricted to participants in each arm who correctly applied the tourniquet). Demographic variables for each intervention arm versus control and retention versus control were compared using Wilcoxon rank sum tests for continuous variables and two-sided Fisher Exact tests for categorical variables.
- f) The data on empowerment will be analyzed using descriptive statistics. Likert type data will be analyzed using non-parametric tests (Wilcoxon sign rank, Kruskal-wallis test). Single group repeated measures analysis will be used to analyze the change in empowerment over time. The Likert type data will also further be analyzed by transforming it into dichotomous categorical data with those reporting being very likely or very comfortable being a positive response and anything less than that being recorded as a negative. The various empowerment parameters will be assessed for their relationship with skill efficacy (correct tourniquet application).

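### The title asks which intervention is most effective, but at initial testing correct application is compared only with control, never between B-Con, audio kit and flashcards.

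*Combined protocol and SAP*

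**What the plan says.** - **Aim.** There is no separate objectives section. The title gives the overall aim: the trial is "to Determine the Most Effective Intervention".
- **Primary outcome at initial testing.** Statistical analysis item a names the main analyses as "pairwise comparisons of the proportion of correct tourniquet application in each of the three intervention arms to the control arm". Item b specifies three two-sided Fisher's exact tests, one per intervention, each against control, as randomized.
- **Sample size (section f, item a).** "Trial arm paired-comparisons were taken as independent trials and sample size was calculated for each pair". The section then states: "The smallest difference in application rate, and the arm used to determine sample size calculation, was between the control and flashcard arm". The rates given are 20% for control and 44% for flashcards. None is given for B-Con or the audio kit. The size is 103 per arm.
- **After initial testing.** The control and prompt arms were trained too: "these individuals then underwent the ACS B-Con training from qualified instructors".
- **Other comparisons.** Item c sets retention results against initial control and against initial B-Con. Item d includes original arm in a model of retention results. Item e compares time across arms, but "restricted to participants in each arm who correctly applied the tourniquet". Item f covers the questionnaires: "Likert type data will be analyzed using non-parametric tests".

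**The concern.** Showing that each of three interventions beats control does not show that any one of them beats another. That needs a direct comparison, and the plan has none for its primary outcome at initial testing.

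The other items do not supply one. By retention testing every arm has had B-Con and no prompts are available, so item d's arm term asks whether the earlier exposure left a trace; the plan itself expects no difference there. Item c has no contrast between interventions. Item e concerns a different outcome in a subset defined after randomization. Item f is not on the primary outcome and does not say that its tests are between arms.

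If all three interventions beat control, readers will look at the three percentages and name a winner. The plan gives them no means of judging whether the ordering exceeds chance.

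**Working it through.** **Inputs.** From section f: 103 per arm, control 20%, flashcards 44%, two-arm comparisons at 0.05. The B-Con and audio rates are not given, so any value used for them is an assumption. Power is for the two-sided Fisher test, summed exactly over all outcome pairs at n = 103:

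Power = Σ Bin(x; 103, p₁) · Bin(y; 103, p₂) · 1[Fisher p(x, y) ≤ α]

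**The plan's own figure.** With p₁ = 0.20, p₂ = 0.44 and mean 0.32, the usual formula gives

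n = [1.96·√(2·0.32·0.68) + 0.842·√(0.20·0.80 + 0.44·0.56)]² / 0.24² = (1.293 + 0.537)² / 0.0576 ≈ 58.1,

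that is 59 per arm, or 67 with continuity correction. The stated 103 is not reproduced. That is a separate matter; the calculations below take 103 as given. Fisher power for 20% vs 44% at 103 per arm is 95.1% (88.7% at 0.05/3).

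**What section f implies for the other two arms.** The wording about pairs can be read in two ways.

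1. *Control pairs only.* Each intervention is at least 24 points from control. A rate 24 points below 20% is impossible, so B-Con and audio are at 44% or more. Gaps between interventions are unconstrained.
2. *All six pairs.* Every gap is at least 24 points. The next rate is then at least 44 + 24 = 68% and the top one at least 92%. Since the top cannot exceed 100%, the middle is at most 76%. B-Con and audio lie at 68–76% and 92–100%, in some order.

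**Chance that all three beat control.** The arms share one control group, so condition on its count c:

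Σ_c Bin(c; 103, 0.20) · Π_j P(arm j significantly better than c)

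| True rates of the three interventions | All three significant at 0.05 |
|---|---|
| 44 / 44 / 44% | 88.4% |
| 44 / 50 / 55% | 94.8% |
| 44 / 60 / 70% | 95.1% |
| 44 / 68 / 92% | 95.1% |

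**How far an ordering can be trusted.** With three equal true rates, the exact distribution of the range of observed proportions gives:

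| Common true rate | Range ≥ 5 points | Range ≥ 10 points |
|---|---|---|
| 44% | 72.0% | 30.3% |
| 68% | 68.9% | 25.9% |

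At assumed true rates of 44, 50 and 55%, the best arm is alone on top in 71.9% of trials. Another arm is alone on top in 20.4% + 2.7% = 23.1%, and there is a tie for top in 5.0%.

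**What head-to-head tests would achieve at 103 per arm.**

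| Pair | Power at 0.05 | Power at 0.05/3 |
|---|---|---|
| 44 vs 55% | 29.0% | 15.9% |
| 44 vs 60% | 57.2% | 39.4% |
| 44 vs 68% | 92.3% | 83.2% |
| 44 vs 70% | 96.0% | 90.0% |
| 68 vs 92% | 99% | 97% |

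From 44%, power of 80% is reached at 64.3% (a gap of 20 points) at 0.05 and at 67.3% (23 points) at 0.05/3. Over the whole six-pair region, on a 1-point grid and for all three pairs, the minimum power is 92.3% and 83.2%, both at 44 vs 68%. The 0.05/3 level is only Holm's first step, so these adjusted figures are lower bounds for each comparison under Holm.

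For 44 vs 55%, the half-width of a 95% confidence interval for the difference is 1.96·√[(0.44·0.56 + 0.55·0.45)/103] ≈ 13.6 points.

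**The case against.** The strongest reply is that the mismatch lies in one phrase of the title. Items a and b and the pair that set the sample size are consistent with a design comparing several arms with a common control, which is legitimate. No hypothesis says that one intervention outperforms another. This stands in part: it is why narrowing the title and conclusions is a full remedy. But the title is the only statement of the aim, and as it reads the plan does not answer it.

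Second, the case of equal arms at 44% is a boundary case on the control-pairs reading and is excluded on the six-pair reading, as is 44/50/55%. That is correct. Those figures show how an ordering can arise by chance, not what the plan expects. The chance that all three arms beat control is high on either reading.

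Third, the counts by arm will exist, so differences could be computed later, and small gaps would often stay unresolved. Both are true. Low power is a reason to show the interval, not to leave an ordering without one.

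Fourth, much of the analysis text is in the past tense, so prespecification may no longer be possible. That affects how the added comparisons are labelled, not whether they are needed.

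**Conclusion.** The concern holds and should be fixed. On correct application at initial testing, only contrasts with control are planned, so the plan followed as written gives no inference on the question in its title. The statement is limited to that outcome and time point; item c, for example, also compares retention with initial B-Con. The wording about pairs in section f does not rescue it, because even on the six-pair reading the analysis section lists no test between interventions.

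With 103 per arm and section f's rates, all three interventions beat control in 88% to 95% of trials, which is the result that leaves the title question open. How well head-to-head tests would settle it depends on rates the plan does not state. Power is at least 92% at 0.05 on the six-pair reading. On the control-pairs reading it could be as low as 29%, or lower, for gaps of 11 points or less from 44%. The three control comparisons themselves are not affected by this point.

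**What to change.** Either of two changes is sufficient.

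1. **Add the comparisons.** In the Statistical analysis section, add B-Con vs audio, B-Con vs flashcards and audio vs flashcards on correct application at initial testing, as randomized. Report each with a risk difference, a 95% confidence interval and a two-sided Fisher test, Holm-adjusted across the three. Make them secondary if specified before results are seen; otherwise label them post hoc and exploratory. Keep the three control comparisons as primary. Base any claim that an arm is most effective on these comparisons, and do not read a non-significant one as equivalence.
2. **Or narrow the claim.** Limit the title and conclusions to efficacy against no intervention. If results are already known, this is the simpler course.

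In either case, state in section f which pairs were sized and give the B-Con and audio rates used.

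**Cost.** Three tests and intervals on outcomes already recorded, or a wording change, plus a short clarification in section f. No new participants. The drawback of the first option is that gaps below about 20 points may stay unresolved, and the honest answer may be that no single best arm was shown. On the six-pair reading this largely disappears (power at least 83% at 0.05/3).

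### Both retention contrasts set only the retested against a full initial arm; apart from one unadjusted demographic comparison, nothing planned addresses selective return, and the skill-decay result is the most exposed.

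*Combined protocol and SAP*

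**What the plan says.** All references are to the combined protocol and SAP.

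- **Who is to be retested.** Under Test for retention, "we planned to test all study subjects with a simulated mass causality scenario for retention of knowledge and skills", 3-9 months after the trial. No expected return rate is given. The only loss allowance, in section f, is 20% for prior training.
- **The two contrasts.** Statistical analysis, item c, plans "all participants tested at retention versus initial control to identify long-term efficacy (correct tourniquet application) compared to no training" and "participants tested at retention versus initial testing in B-Con randomized arm to identify if there is a significant skill decay". Neither reference group is limited to people who came back. The second contrast does not say whether the retested are drawn from all four arms or from the B-Con arm alone.
- **The method.** "Generalized estimating equations z-tests were used in these pairwise tests to account for the repeated measures on participants" who were in both phases. This implies that some may be in only one.
- **Training sequence.** Section i: "After testing of the two point of care prompt arms and the control arm, these individuals then underwent the ACS B-Con training".
- **Neighbouring analyses.** Item d: "an a priori planned logistic regression analysis was performed to identify any demographic associations with correct tourniquet application", fitted at retention. Item e: "Demographic variables for each intervention arm versus control and retention versus control were compared using Wilcoxon rank sum tests for continuous variables", with Fisher tests for categorical variables. Item f: "The various empowerment parameters will be assessed for their relationship with skill efficacy (correct tourniquet application").

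**The concern.** A change between two time points can be read as decay only if the people measured later represent those measured earlier. Here the later group is whoever returned and the earlier group is a whole randomised arm. If better performers return more readily, decay is understated. If worse performers do, decay is overstated. GEE with a robust variance corrects the standard error for within-person correlation; it does not in general remove this bias.

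Items d and f do not fill the gap. They show whether a characteristic predicts success, not whether it predicts return. Item e comes closest. Because the arms were randomised, a demographic imbalance between the retested and control would be a partial signal of selective return for the efficacy contrast. But it does not compare returners with non-returners, covers neither initial test result nor willingness and comfort, offers nothing for the B-Con reference, and adjusts nothing. Returning controls also sit on both sides of tests that assume independent groups.

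At stake is the statement about whether skill decays after B-Con. Only the B-Con arm has an immediate post-B-Con score, so the pooled and B-Con-only readings of the second contrast also differ in meaning and in precision.

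**Working it through.** **Inputs from the documents.** 103 per arm and 412 in total; control rate 20%; flashcard rate 44% (section f). No size or power is stated for the retention contrasts, so there is no planned retention figure to reproduce. The 103 is taken as given. (The stated 20% versus 44%, 80% power and two-sided 5% give 59 per arm, or 67 with continuity correction. That is a separate matter.)

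**Assumptions.** Return 50-80%; initial B-Con rate 70-80%; within-person correlation 0.2; true decay 15 points; the selection strengths in step 2.

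**1. Bias identity.** Bias in the retention rate = (1 − return) × (returner minus non-returner success). For gaps of 5 to 20 points the range runs from 0.2 × 5 = 1 point to 0.5 × 20 = 10 points. Ten points needs both 50% return and a 20-point gap; at 80% return the maximum is 0.2 × 20 = 4.

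**2. A moderate mechanism.** Exact summation over arm, initial result and a binary willingness trait (prevalence 0.5). Initial success is 20% control, 44% flashcard, 44% audio (assumed) and 80% B-Con (assumed); overall retention success is 55-65%. Willingness has log-odds 0.7, and initial result log-odds 1.0, on both return and retention success.

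| Overall return | Pooled bias, both drivers | Willingness only |
|---|---|---|
| 50% | 3.8-4.1 points | 1.4-1.5 |
| 60% | 3.0-3.3 | 1.1-1.2 |
| 80% | 1.5-1.6 | 0.5-0.6 |

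For B-Con participants alone, both drivers give 0.9-2.6 points over this range of return.

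**3. Power for a true 15-point decay, pooled reading.** With p0 the initial B-Con rate, pR the expected observed retention rate, nR = 412 × return and nB = 103 × return:

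Variance = p0(1 − p0)/103 + pR(1 − pR)/nR − 2 × nB × 0.2 × √[p0(1 − p0)pR(1 − pR)]/(103 × nR).

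Power = Φ(|p0 − pR|/SE − 1.96).

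Example: p0 = 0.70, 50% return, nR = 206, nB = 51.5.
- No bias, pR = 0.55: variance 0.00204 + 0.00120 − 0.00022 = 0.00302; SE 0.0549; z = 0.15/0.0549 = 2.73; power 78%.
- Four points of bias, pR = 0.59: SE 0.0547; z = 0.11/0.0547 = 2.01; power 52%.

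| Return | Bias used | Power, no bias | Power, with bias |
|---|---|---|---|
| 50% | 4 points | 78-86% | 52-61% |
| 60% | 3 | 81-88% | 62-72% |
| 80% | 1.5 | 84-91% | 76-85% |

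The ranges cover p0 from 0.70 to 0.80. On the B-Con-only reading (nR about 52-82), power is about 50-71% before any bias, so sampling error is a major limit there too.

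**4. Efficacy contrast.** Take retention success of 55%, the lower end of what these scenarios imply, 50% return, control 20%, correlation 0 and the largest downward bias in step 1 (10 points). The observed difference is 45 − 20 = 25 points; SE = √(0.16/103 + 0.2475/206) = 0.0525; z = 4.76; power above 99%.

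**5. Item e's overlap.** The independent-groups variance is proportional to 1/nR + 1/103. With equal return by arm the true variance is smaller by 2/412. At 50% return, 0.01456 against 0.00971 moves the critical value from 1.96 to 2.40, a true size of 1.6% for a nominal 5% test. At 80% return it is 1.3%. The one partial diagnostic is therefore blunted.

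**6. Bounds.** If a share r returns and a proportion p of them succeed, full-cohort success lies between r × p and r × p + (1 − r). With p = 50%: 25-75% at 50% return, 40-60% at 80%.

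**The case against.** - **Everything that drives the size is assumed.** This stands. The documents give no return rate, B-Con rate, correlation or selection strength, and they plan to retest everyone. Selection on initial result is itself uncertain, because participants had no feedback during the test and three arms were trained afterwards. With selection on one trait only, the bias is 0.5-1.5 points. The illustration shows that the problem can matter, not that it did.
- **A reader might infer that nothing planned touches selective return.** Item e does, in part, for the efficacy contrast. The gap is what remains beyond it.
- **A reader might infer that the long-term efficacy conclusion is equally at risk.** The figures do not support this. Ten points of downward bias would cut power for a true 15-point gain from 83% to 17%, but that needs retention success of 35%, 50% return, and worse performers returning with a 20-point gap. The decay scenarios used here put retention at 55-65%. Section f's smallest expected difference, for the initial test, is 24 points; at a gain of that size, power is still 97% with 4 points of bias.
- **A reader might apply 4 points of bias at every return rate.** The mechanism gives about 4 only at 50% return. At 80% it gives about 1.5, and 4 there requires the extreme 20-point gap.
- **Items a to e are in the past tense, so the plan may be beyond amendment.** The documents do not settle this. It affects how the additions are labelled, not whether they are useful.

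**Conclusion.** The point holds for the non-randomised retention contrasts, chiefly skill decay. Followed as written, item c can give a biased decay estimate with no planned means of detecting or adjusting for it beyond a limited demographic comparison. Neither direction nor size can be determined from the documents. Under the assumed moderate selection, the loss of power for a 15-point decay is serious at 50-60% return (roughly 16 to 26 percentage points) and modest at 80% (roughly 6 to 8). If selection ran the other way, the same bias would exaggerate decay. The randomised initial-phase comparisons, which are the main analyses, are unaffected. This should be fixed, but it does not threaten the trial's primary conclusion. Confidence is medium, because the text is clear and the size is not.

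**What to change.** 1. Report the return rate by arm and by initial result. Add a returner versus non-returner table on demographics, prior first-aid training, initial result and baseline willingness and comfort. Treat item e's retention-versus-control comparison as descriptive, since its groups overlap.
2. Keep the planned GEE contrasts. Add, as sensitivity analyses of both, an inverse-probability-of-return weighted GEE and the simple bounds of step 6 for unmeasured selection. Model return on arm, initial result, their interaction, demographics, prior first-aid training and willingness/comfort. The interaction is needed because the initial test was untrained, prompt-aided or post-training depending on arm. Give initial records weight 1, and use an independence working correlation with robust standard errors.
3. State whether the decay contrast pools all arms. Beside it, report a within-person (paired) analysis of B-Con-arm participants with both tests. An unweighted B-Con-only contrast is not enough, because it still compares returners with everyone initially tested.

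If the analyses are already done, report these as post hoc sensitivity analyses.

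**Cost.** This is a cheap improvement: some wording, one table and a few extra analyses on data already collected. In simulation under the step 2 mechanism, weighting raised the standard deviation of the estimates by 0-6%. Weighting corrects only for measured predictors of return: with willingness left out of the weights, about 0.3-1.2 points of bias remained. The B-Con-only analysis is less precise, and the paired result applies only to those who returned.

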- a. After the hemorrhage control test, all participants were given a post-trial questionnaire which assessed their perception of usefulness of the training, willingness and self-reported comfort-level in providing first response in a mass causality scenario on a Likert-type scale.
- b. Questionnaires will also be re-administered at 3-9 month retention testing, which will assess participant perception of usefulness of the training, self-reported willingness and comfort-level in providing first response in a mass causality scenario on a Likert-type scale as well as other questions relating to emergency preparedness and hemorrhage control.

i. Protocol:

- a. A reviewer will read aloud a simulated scenario describing an explosion in a public gathering. A bleeding mannequin with traumatic amputation of leg just above the knee will be present. The participant will then be directed to a nearby bleed-control box and asked to stop the bleeding. The bleed-control box will contain a combat application tourniquet (CAT). The reviewer will start timing after directing the subject to the bleed-control box.

Subjects in the control arm were directly subjected to the bleeding control test. Experimental arm 1 subjects will attend B-Con course taught by ACS trained instructors and then subjected to the test. Experimental arm 3 and 4 subjects received an audio guide and flash card in their bleed-control box respectively,

during the test. At retention testing, participants were not retrained nor had available point of care prompts.

The participants were timed until they feel that they had stopped the bleeding. Time for complete bleeding control and tourniquet application was recorded only for subject who appropriately control the hemorrhage within 7 minutes. Appropriateness of hemorrhage control was determined by correct placements of tourniquet and adequate pressure of the tourniquet as determined by attempting to forcefully slide a Kelly clamp under between the tourniquet and the extremity of the mannequin. For unsuccessful hemorrhage control, the reason for failure was recorded. No feedback was given to the participant during the test.

- b. 20 reviewers were used for the purpose of this study. All the reviewers were physicians, nurses, and EMTs, trained in hemorrhage-control.

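### Item e tests time to correct application only among participants who succeeded, so the test mixes speed with who succeeds and is not a randomized comparison of speed

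*Combined protocol and SAP*

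**What the plan says.** Statistical analysis item a sets the endpoint: "The primary outcome in our study was the correct application of tourniquets". Item b compares the proportions by Fisher's exact test, "three interventions to control in an intent-to-treat analysis (as randomized"). Item e then uses a Wilcoxon rank sum test to "compare time to correct tourniquet application across arms (restricted to participants in each arm who correctly applied the tourniquet").

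Section i (Protocol), item a, explains why failures cannot enter that test: "Time for complete bleeding control and tourniquet application was recorded only for subject who appropriately control the hemorrhage within 7 minutes".

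Section f (Sample size calculation) gives the success rates the plan expects: "Control group expected application rate 20% based on prior studies" and "Flashcard Proportion expected application rate 44% based on prior studies". It describes this pair as having the smallest difference, and concludes: "Final sample size is 412 with 103 subjects in each arm".

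No section gives a time analysis that keeps the failures, and item e gives no caution on how to read the restricted comparison.

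**The concern.** Randomization balances the arms as allocated. It does not balance the subsets that later succeed when the intervention changes who succeeds. If prompts or training bring in people who would have failed unaided, the experimental successes include a kind of participant who is absent from the control successes.

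The between-arm p-value for time then reflects two things at once: any change in speed and the change in membership. If the added successes are slower than the rest, an intervention that slows nobody can look slower. If they are faster, it can look faster. If they are equally fast, there is no distortion. At stake is what the trial may conclude about speed, for instance a report that a prompt delays bleeding control when it has only helped more people to achieve it.

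**Working it through.** **Inputs from the documents.** Expected success is 20% (control) and 44% (flashcard), with 80% power, alpha 0.05 and 103 per arm (section f); tests are two-sided (item b). I take 103 as the number analysed per arm.

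**The plan's own figure.** With pooled proportion 0.32,

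n = [1.960·√(2·0.32·0.68) + 0.8416·√(0.20·0.80 + 0.44·0.56)]² / 0.24² = 58.1, so 59 per arm.

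With continuity correction, n = (58.1/4)·[1 + √(1 + 4/(58.1·0.24))]² = 66.2, so 67 per arm. The stated 103 is not reproduced. The same formulas return 103 at a flashcard rate of about 37.6% (uncorrected) or 38.6% (corrected). That discrepancy is a separate matter. Here it means only that 44% is not firm, so I carry both rates.

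**Who is in the test.** Control: 103 × 0.20 = 20.6. Flashcard: 103 × 0.44 = 45.3. The test leaves out about 80% of one arm and 56% of the other.

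**How far membership must differ.** The share of people who would succeed under both conditions cannot exceed 20%. So

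P(would succeed as control | succeeds with flashcard) ≤ 0.20/0.44 = 45.5%,

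and at least 54.5% of flashcard successes would have failed as controls: 103 × (0.44 − 0.20) = 24.7, about 25 of 45. At 37.6% the bound is 1 − 0.20/0.376 = 46.8%; at 38.6% it is 48.2%. This measures membership, not bias.

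**What it could do to the test: an assumed model.** The documents give no distribution of times, so everything in this step is an assumption. Ability A is standard normal. A participant succeeds if ρA + √(1−ρ²)·e exceeds the cut-off that gives the arm's rate. Log time is slope·A plus residual error, identical in both arms, so nobody's speed is affected. The 7-minute limit is not modelled. The test is a two-sided Mann-Whitney at 5% on successes only, with 103 per arm and 10,000 trials per cell (Monte Carlo standard error 0.2 to 0.4 points). Cells show total rejection, with rejections calling flashcard slower in brackets; the nominal values are 5% (2.5%).

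| Residual SD, slope | ρ = 0.3 | ρ = 0.6 | ρ = 0.8 |
|---|---|---|---|
| 0.5, −0.1 | 5.0% (3.1%) | 5.7% (4.1%) | 5.6% (4.4%) |
| 0.5, −0.3 | 5.8% (4.6%) | 8.7% (8.1%) | 11.9% (11.7%) |
| 0.25, −0.1 | 5.3% (3.9%) | 6.8% (5.9%) | 8.1% (7.5%) |
| 0.25, −0.3 | 6.9% (6.0%) | 14.5% (14.3%) | 26.2% (26.1%) |

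Checks at ρ = 0.6, for SD 0.5 and 0.25 respectively:
- No ability-time link (slope 0): 4.9% and 5.3%.
- Equal success, 20% in both arms, slope −0.3: 5.1% and 4.1%.
- Slope +0.3: 9.0% and 14.7%, now nearly all calling flashcard faster.
- Flashcard rate 38.5%, slope −0.3: 7.5% and 11.3%.

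A harsher assumed model, in which ability alone decides success, gives total rejection of 8%, 15%, 35% and 75% at ability-time correlations of 0.3, 0.5, 0.7 and 0.9 (5,000 trials each). The spread between the two models shows how little the documents constrain the size.

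**The case against.** Time to correct application does not exist for someone who never applied the tourniquet correctly, so some restriction is built into the quantity. The plan states the restriction openly, attaches no hypothesis or decision to time, and does not call the result a randomized effect. A labelled comparison among successes is a usable description. Under weak dependence the nominal 5% is nearly kept: 5.0% to 6.9% at ρ = 0.3.

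All of this stands, and it limits the point to a missing caution and a missing companion analysis. It does not remove the point: saying which participants were tested does not tell a reader that the test has lost the protection of randomization. Keeping or dropping the p-value is a matter of preference, provided it is labelled.

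A reader might infer that item e breaks the plan's intent-to-treat commitment. The documents do not support that: item b attaches the as-randomized principle to the Fisher tests only. A reader might also infer that the time test is shown to be biased against the interventions. That is not supported either. The 54.5% bound concerns membership, and the direction reverses with the sign of an ability-time relation on which the documents are silent.

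**Conclusion.** The point holds as a secondary one. Item e compares groups defined by the primary outcome, and the plan expects that outcome to differ by arm. At least 54.5% of flashcard successes (47-48% if the rate is nearer 38%) would have no counterpart among control successes. The rates cover control versus flashcard only; the plan calls this the smallest difference, so the other arms should differ from control by at least as much.

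Reading the p-value as an effect on speed needs success to be unrelated to underlying speed, and the documents give no basis for that. The size and direction of any error are undetermined. The rejection rates above illustrate a range and are not estimates for this trial. With a negative slope, all the excess falls in the slower direction. The comparison of success proportions in item b is unaffected.

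**What to change.** In item e:

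1. Add the cumulative incidence of correct control from 0 to 7 minutes by arm, as randomized. At each time this is the number with correct control by then, divided by everyone analysed in the arm. Failures stay in the denominator and never reach the event. Use the plan's analysis set after the exclusion in section d: "Anyone with previous formal hemorrhage control or tourniquet training was excluded from the trial analysis". Make this curve the basis for any between-arm statement about time to control.
2. Report success-only times (median, IQR) beside the success proportions. Label any Wilcoxon p-value kept for them as conditional on success and not a randomized comparison of speed.
3. State whether a correct application after 7 minutes counts as success. Section i ties the limit to the recording of time, while item a defines the primary outcome with no limit. The curve's 7-minute value equals the primary proportion only if later applications do not count.

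I would not add a rank test with failures placed last. In the same model (ρ = 0.6, slope −0.3) it agrees with Fisher's test in 97-98% of trials when speed is unchanged, so it largely repeats the primary analysis.

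The cost is some wording and one figure, from data already recorded. The drawbacks are that the curve itself mixes success with speed, and that the time p-value can no longer be read as an effect on speed. Item e is written in the past tense, so anything added after the data were seen should be labelled post hoc.
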